### **12.2 Serious Adverse Events**

During clinical investigations, AEs may occur which, if suspected to be IMP related, might be significant enough to lead to important changes in the way the IMP is developed (e.g., change in dose, population, monitoring need, consent/assent forms). This is particularly true for events that threaten life or function. Such SAEs will be reported promptly to Regulatory/Competent Authorities, applicable IRB/ECs and investigators (expedited reporting) by GW.

An AE must only be classed as serious, i.e., a SAE, when the event falls into one of the following criteria:

- Results in death.
- Is life-threatening.\*

- Requires inpatient hospitalization or prolongation of existing hospitalization.
- Results in persistent or significant disability/incapacity.
- Is a congenital anomaly/birth defect.
- Is medically significant.\*\*

\* The term “life-threatening” in the definition of “serious” refers to an event in which the patient was at risk of death at the time of the event; it does not refer to an event, which hypothetically might have caused death if it were more severe.

\*\* Medical and scientific judgment should be exercised in deciding whether SAE reporting is appropriate in other situations. Important medical events may not be immediately life threatening or result in death or hospitalization but may jeopardize the patient or may require intervention to prevent one of the other outcomes listed in the definition above. These should also usually be considered serious. Examples of such events are intensive treatment in an emergency room or at home for allergic bronchospasm; blood dyscrasias or convulsions that do not result in hospitalization; or development of drug dependency or drug abuse.

### 12.3 Reporting Procedures for Serious Adverse Events

All SAEs occurring during the study must be reported to GW with any other supporting information and recorded in the AE section of the CRF. Any on-going SAEs should be followed up until resolution wherever possible. For all deaths, the working diagnosis or cause of death as stated on a death certificate, available autopsy reports and relevant medical reports should be sent to GW promptly.

**All SAEs must be reported directly to GW PVD within 24 hours of discovery or notification of the event.** All SAE information must be recorded on the SAE forms provided in the site files and faxed to GW PVD. Additional information received for a case (follow-up or corrections to the original case) need to be detailed on a new SAE form, signed/dated and faxed to the GW PVD and the AE section of the CRF must be updated.

The investigator should continue to document all AEs which occur up to the last formal follow-up observational period (Visit 10). If the investigator subsequently becomes aware of a new IMP-related SAE after the last formal follow-up period of the study, these should still be reported to the GW PVD.

Any other problem discovered outside these time limits which is deemed to be an unexpected safety issue and is likely to have an impact on patients who have participated in the study, then these should be treated as an SAE and reported to GW PVD. Such post study SAEs do not need to be recorded on the patient's CRF if editing rights to the CRF have been removed.

Contact details for the GW PVD are provided at the front of the site files for all study centers, and upon the GW SAE Report form.

## 12.4 Pregnancy

Any patient, or patient's partner, who has become pregnant whilst receiving IMP, or within 90 days of last dose of IMP, must be reported to the GW PVD within 24 hours of first awareness. Please use the GW Pregnancy Monitoring Forms provided. Where possible the investigator should provide the outcome of the pregnancy.

The investigator is not obliged to actively monitor for any pregnancies that commence more than 90 days after the final dose of IMP. However, if the investigator becomes aware of a new pregnancy outside this time limit then they should report it as above. GW PVD will follow-up for all pregnancy outcomes.

## 12.5 Causality Assessment

Causality assessment is required for all AEs and SAEs. Causality assessment must only be assigned by the investigator. All cases judged as having a reasonable suspected causal relationship to the IMP must be reported as such. The expression "*reasonable causal relationship*" is meant to convey in general that there are facts (evidence) or arguments to suggest a causal relationship.

The following question which must be answered by the investigator for all AEs is used to capture the reasonable causal relationship of an event to the IMP:

*"In your opinion is there a plausible relationship to the IMP?"* The answer is "yes", or "no".

Events that start before the first dose of IMP (pre-treatment) should be considered as not causally related. Where a pre-treatment event worsens in severity following the first dose of IMP a new event record should be entered into the CRF.

Considering the explanation given above, investigators are strongly encouraged to express their opinion on what the cause of an AE might be. For individual patients, the

investigator is usually in the best position to assess the underlying suspected cause of an AE. For all AEs and especially SAEs, it is important that the investigator assess not only the possible role of the IMP but also competing etiological factors as the underlying cause. Factors for consideration may include:

- Medical history.
- Lack of efficacy/worsening of treated condition.
- Concomitant or previous treatment.
- Withdrawal of IMP.
- Protocol-related procedure.

## 12.6 Reporting Procedures for All Adverse Events

All AEs\* (including SAEs) occurring during the study will be reported on the running logs in the AE section of the CRF. This includes all events from the time following screening (Visit 1) to post study follow-up (Visit 10), whether or not attributed to IMP and observed by the investigator or patient.

\*For the patient's expected seizure types, these do not routinely require documentation as AEs. However, any worsening, including change in the pattern or severity of seizures, must be documented as an AE. Any AE which meets SAE criteria should still be reported as a SAE.

The following information will need to be provided for all AEs:

### **A) Adverse Event (diagnosis or syndrome if known, or signs and symptoms)**

Where the investigator cannot determine a diagnosis, signs or symptoms should be recorded on the AE section of the CRF. Once a diagnosis has been determined the AE section of CRF must be updated to reflect the diagnosis in replacement of the original symptoms. In circumstances where only a provisional diagnosis is possible (working diagnosis), the CRF must be updated to reflect the provisional diagnosis in replacement of the original symptoms. In some circumstances it may be relevant for the investigator to include the symptoms alongside the diagnosis in the verbatim event description. However, the diagnosis (full or provisional) should be clearly stated e.g., fever and malaise due to a respiratory tract infection.

## **B) Adverse Event Start Date and Stop Date**

The start and stop dates of the event must be provided. All AEs require these fields to be completed in full. Partial dates or missing dates are not normally acceptable and significant effort must be undertaken to obtain any unknown information. If a precise date is not known an estimated date should be provided instead. When a complete date cannot be given then record as much information as possible (i.e., month and year or in exceptional circumstances just year). When the actual start date becomes known the CRF must be updated to replace the previously recorded date.

## **C) Outcome**

The outcome of the event must be recorded accurately and classified into one of the following categories:

- Recovered.
- Recovered with sequelae.
- Continuing.
- Patient died.

## **D) Severity**

When describing the severity of an AE the terms mild, moderate, or severe should be used. Clinical judgment should be used when determining which severity applies to any AE.

If the severity of an AE fluctuates day-to-day, for example, a headache or constipation, the change in severity should not be recorded each time, instead only the worst observed severity should be recorded with AE start and stop dates relating to the overall event duration regardless of severity.

A severe AE is not the same as a SAE. For example, a patient may have severe vomiting but the event does not result in any of the SAE criteria above. Therefore it should not be classed as serious.

## **E) Causality**

See [Section 12.5](#) above.

## **F) Action Taken with Study Medication**

This question refers to the action taken with the IMP due to an AE. The action with the IMP must be classed as:

- None.
- Dose reduced temporarily.
- Dose reduced.
- Study medication interrupted.
- Study medication stopped.

## **12.7 Follow-up Procedures for Adverse Events**

The investigator may be asked to provide follow-up information to the GW PVD for any AEs reported.

AEs considered related to the IMP by the investigator or the sponsor should be followed up until resolution or the event is considered stable.

It will be left to the investigator's clinical judgment whether or not an AE is of sufficient severity to require the patient's removal from treatment. A patient may also voluntarily withdraw from treatment due to what he or she perceives as an intolerable AE; further details of withdrawal are presented in [Section 10](#). If either of these occurs, the patient must undergo an end of treatment assessment and be given appropriate care under medical supervision until symptoms cease or the condition becomes stable.

## **12.8 Potential Cases of Drug-Induced Liver Injury**

All investigational sites are required to submit to the GW PVD the laboratory results for any patient after randomization that meet the criteria for the selected laboratory parameters as follows:

- ALT or AST  $>3 \times$  ULN with the appearance of fatigue, nausea, vomiting, right upper quadrant pain or tenderness, fever, rash, and/or eosinophilia ( $>5\%$ ).
- ALT or AST  $>8 \times$  ULN.
- ALT or AST  $>5 \times$  ULN for more than two weeks.
- ALT or AST  $>3 \times$  ULN **and** (TBL  $>2 \times$  ULN **or** INR  $>1.5$ ).

These reports must be sent to the GW PVD using the same fax number for SAE reporting within 24 hours of becoming aware of the results. In addition, please send a copy of the patient's baseline laboratory results with all reports to GW PVD.

Abnormal values in AST and/or ALT concurrent with abnormal elevations in TBL that meet the criteria outlined above are considered potential cases of drug-induced liver injury and will be considered as protocol defined criteria for withdrawal and important medical events. The investigator will arrange for the patient to return to the investigational site as soon as possible (within 24 hours of notice of abnormal results) for repeat assessment of ALT, AST, TBL and alkaline phosphatase levels, detailed history and physical examination; patients should be followed in this way until all abnormalities have normalized (in the investigator's opinion) or returned to the baseline state.

Elevations in ALT or AST  $>3 \times \text{ULN}$  or TBL  $>2 \times \text{ULN}$  alone are not considered potential cases of drug-induced liver injury, but will be followed as detailed above, within 72 hours' notice of abnormal results. If the patient cannot return to the investigational site, repeat assessments may be done at a local laboratory and the results sent to GW PVD.

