Investigators at study sites will be notified of safety laboratory test results. All laboratory results will be reviewed and the reports signed by an investigator. Any results considered to be of clinical significance must be addressed and followed up as clinically appropriate. See [Section 12.8](#) for guidance on evaluation of potential drug induced liver injury. All laboratory results considered to represent an AE must be documented on the CRF.

Repeat samples will be taken, if required, for clinical follow-up or if the sample is lost or damaged. Any abnormal end of treatment clinical laboratory result of clinical significance must be repeated at regular intervals until it returns to normal, or until an investigator is satisfied that the abnormality is not related to the IMP and needs no further investigation.

Sample volume requirements and processing procedures will be detailed in a separate laboratory manual. The patient/caregiver must be advised that it may not be safe for the patient to undertake further blood tests within one month of any study-related blood draws and to inform the investigator if they suffered any blood loss during the one-month period leading up to a planned blood draw.

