### **9.2.8 Visit 8 (Day 99, End of Treatment/Withdrawal Visit)**

This visit will occur 98 days after randomization (Visit 2) or earlier if the patient withdraws from the study. A visit window of  $\pm 3$  days from the scheduled visit date is permitted, but it is preferred that the visit is performed on the scheduled visit day where possible. Patients will be instructed to record the dosing time of their concomitant AEDs in the diary. They will also be asked to record their meal times the day before and the day of Visit 8.

The following assessments will be made at Visit 8 / the Withdrawal visit: vital signs, physical examination (including height and body weight), ECG, EDSS, Sleep Disruption 0–10 NRS, CGIC, CGICSD, QOLCE, C-SSRS (Children's Since Last Visit), cognitive assessment battery (at participating sites), details of menstruation (for females), Tanner Staging (for patients aged 10–17 [inclusive], or earlier if clinically indicated by onset of menarche or other signs of precocious puberty) and the Vineland-II. The Caregiver Impression of IMP Palatability will also be assessed. Clinical laboratory samples (blood and urine [where possible]) will be taken for hematology, biochemistry, urinalysis, a urine THC screen (required), determination of serum IGF-1 levels and a pregnancy test (using a serum sample, as appropriate). The patient's IVRS report and paper diary will

be reviewed and the information recorded along with information regarding AEs, epilepsy-related hospitalizations, concomitant medications and/or changes to medication (including AEDs). The investigator must assess adherence to the dosing regimen.

Prior to the final dose of maintenance IMP, blood samples will be taken to determine plasma concentrations of CBD and its major metabolites (only patients who weigh  $\geq 20$  kg) and, provided the risk/benefit outcome is favorable in the investigator's opinion, concomitant AEDs (all patients). The final maintenance dose of IMP will then be taken in the clinic. ECG and vital signs will be re-assessed two to three hours post-dose. Further blood samples will be taken for CBD PK analyses. The presence of THC in plasma will also be assessed at a single time point (two to three hours post-dose). A urine sample will be collected (complete void) at the time of first blood sample collection for both CBD and THC analysis, and the exact urine volume will be recorded. See [Section 9.1.10](#).

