## 10 WITHDRAWAL

In accordance with the Declaration of Helsinki, the FDA regulations relating to good clinical practice (GCP) and clinical trials, the EU Clinical Trials Directive (2001/20/EC) and/or other applicable regulations, a patient has the right to withdraw from the study at any time and for any reason without prejudice to his or her future medical care by the physician or at the institution.

The patient must be withdrawn from the study if any of the following apply:

- Administrative decision by the investigator, GW, or a Regulatory Authority.
- Pregnancy.
- Protocol deviation that is considered to potentially compromise the safety of the patient.
- Withdrawal of patient consent/assent.
- Withdrawal of parent(s)/legal representative consent.
- Lost to follow-up.
- ALT or AST  $>3 \times$  ULN with the appearance of fatigue, nausea, vomiting, right upper quadrant pain or tenderness, fever, rash, and/or eosinophilia ( $>5\%$ ).
- ALT or AST  $>8 \times$  ULN.
- ALT or AST  $>5 \times$  ULN for more than two weeks.
- ALT or AST  $>3 \times$  ULN and (TBL  $>2 \times$  ULN or INR  $>1.5$ ).

Patients may also be withdrawn from the study for any of the following:

- Patient non-compliance.
- AE which, in the opinion of the investigator, would compromise the continued safe participation of the patient in the study.
- Any evidence of drug abuse or diversion.
- Suicidal ideation or behavior of type four or five during the treatment period, as evaluated with the C-SSRS.

Should a patient request or decide to withdraw from the study, all efforts must be made to complete and report the observations as thoroughly as possible up to the date of

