withdrawal. Patients who withdraw should have their dose of IMP tapered gradually (10% each day) over a period of 10 days, beginning at the time the decision is made to discontinue. In some cases, tapering the dose of IMP may be inadvisable (e.g., continued dosing is not possible due to an AE). The decision on whether or not to taper IMP will be left to the investigator's clinical judgment. All assessments required at Visit 8 / the Withdrawal visit should be conducted if possible. If the tapered dose is administered, patients should continue to complete the IVRS and paper diary and return for Visit 9, if possible. For patients who begin to taper IMP but subsequently withdraw, Visit 9 assessments (including ECG and clinical laboratory sampling) should be conducted, if possible; this visit should occur on the final day of dosing or as soon as possible after this date. Patients withdrawing due to an AE should be followed up according to [Section 12.7](#) safety follow-up visit. All information should be reported on the applicable CRF pages (refer to [Section 9.1](#)). Wherever possible, the safety follow-up visit should be conducted 28 days from the date of the last dose of IMP (refer to [Section 9.2.10](#)).

---

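### Protocol Section 12.8 gives liver-injury status only to transaminase rises with raised bilirubin, although Section 10 requires withdrawal for four liver criteria, most of which need no raised bilirubin.

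*Protocol*

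**What the plan says.** Section 12.8 of the Protocol has three parts.

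- **The list.** Four criteria are given: ALT/AST above 3 × ULN with symptoms or eosinophilia; above 8 × ULN; above 5 × ULN for more than two weeks; and above 3 × ULN with either TBL above 2 × ULN or INR above 1.5. Results meeting any of them must reach the sponsor's pharmacovigilance department "within 24 hours of becoming aware of the results".
- **The definition and return.** The class of potential drug-induced liver injury is given to "Abnormal values in AST and/or ALT concurrent with abnormal elevations in TBL that meet the criteria outlined above". The same sentence counts those cases as withdrawal criteria and important medical events. The next sentence has the investigator bring the patient back within 24 hours "for repeat assessment of ALT, AST, TBL and alkaline phosphatase levels, detailed history and physical examination".
- **The exception.** ALT/AST above 3 × ULN or TBL above 2 × ULN "alone are not considered potential cases of drug-induced liver injury, but will be followed as detailed above, within 72 hours" of notice.

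Section 10 repeats the same four criteria under the rule "The patient must be withdrawn from the study if any of the following apply". Section 9.1.9 sends sites to 12.8 "for guidance on evaluation of potential drug induced liver injury".

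**The concern.** Only one branch of one listed criterion mentions bilirubin, yet the definition that follows the list requires it. A site reading 12.8 as its working instruction could therefore record ALT above 8 × ULN with normal bilirubin as something other than potential liver injury, and as neither a withdrawal criterion nor an important medical event, while Section 10 requires that patient to be withdrawn.

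Two things are at stake. One is consistent classification of liver events across approximately 30 centers (Section 4.2). The other is how soon a patient who meets a mandatory liver withdrawal criterion is rechecked. The repeat tests named in 12.8 also leave out INR, although INR above 1.5 is one of the triggers.

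**Working it through.** There is no statistical figure to reproduce. The check sets each listed result, with TBL normal, against Section 10 and the three parts of 12.8.

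Two sentences in 12.8 can each be read in two ways.

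- **The 24-hour return sentence.** *Narrow*: it continues the definition and covers only cases with raised TBL. *Broad*: it has no bilirubin condition of its own and covers every listed result.
- **The exception sentence.** *Literal*: any ALT/AST above 3 × ULN with nothing else is *alone*, however high or prolonged. *Limited*: *alone* means that none of the four criteria is met.

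| Result | Section 10 | Report to sponsor | Named as liver injury in 12.8? | Narrow + literal | Narrow + limited | Broad + limited |
|---|---|---|---|---|---|---|
| > 8 × ULN, TBL normal | withdraw | 24 h | no | 72 h | not stated | 24 h |
| > 5 × ULN for > 2 weeks, TBL normal | withdraw | 24 h | no | 72 h | not stated | 24 h |
| > 3 × ULN + symptoms/eosinophilia, TBL normal | withdraw | 24 h | no | not stated | not stated | 24 h |
| > 3 × ULN + INR > 1.5, TBL normal | withdraw | 24 h | no | not stated | not stated | 24 h |
| > 3 × ULN + TBL > 2 × ULN (comparison) | withdraw | 24 h | yes | 24 h | 24 h | 24 h |

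The last three columns give the patient's return time. The fourth combination, broad and literal, would give the first two rows both 24 and 72 hours, which contradict each other.

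**Classification.** The fourth column does not depend on either choice, because the definition sentence names raised TBL outright. Four results that require withdrawal under Section 10 are not given liver-injury or withdrawal-criterion status in 12.8. Under the literal reading, two of them are expressly denied liver-injury status.

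**Recall time.**

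- Narrow and literal: two results at 72 hours and two with no stated time. The largest difference is 72 − 24 = 48 hours.
- Narrow and limited: no result at 72 hours and four with no stated time. The 48-hour figure does not arise.
- Broad and limited: all four at 24 hours, so no difference.

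These are counts of listed results, not of patients.

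**Consistency with the rest of the plan.** Exclusion criterion 6.2.17 accepts symptoms, or INR above 1.5, beside ALT/AST above 3 × ULN without requiring raised bilirubin. The liver table in SAP Section 5.6.3.1 treats bilirubin above 2 × ULN and INR above 1.5 as alternatives. The bilirubin-only definition in 12.8 is the odd one out.

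**The case against.** The strongest reply is that the practical protections already cover everyone. All four criteria trigger reporting within 24 hours and mandatory withdrawal. At withdrawal, "All assessments required at Visit 8 / the Withdrawal visit should be conducted if possible", and under Section 9.2.8 blood and urine samples "will be taken for hematology, biochemistry, urinalysis, a urine THC screen (required), determination of serum IGF-1 levels"; prothrombin time is part of the panel in Table 9.1.9-1. Section 9.1.9 requires clinically significant results to be followed up, and abnormal end-of-treatment results to be repeated. It also allows repeat samples for clinical follow-up, so the four tests named in 12.8 need not be exclusive. Section 12.7 requires an end-of-treatment assessment and supervised care for patients removed from treatment because of an adverse event. Section 12.2 lets medical judgment class any event as serious.

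It can also be said that the return sentence naturally covers the whole list above it, that a result listed separately as reportable is hardly *alone*, and that 72 hours is a limit rather than a planned delay.

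Most of this stands. It removes any claim that these patients go unreported, untested or unwithdrawn, and it makes the 48-hour difference conditional. It does not remove the classification mismatch, which lies in the definition sentence. Nor does it settle the recall time: none of the general follow-up rules sets an hour limit, and the Withdrawal-visit assessments are to be done only where possible.

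**Conclusion.** The point holds as a minor safety-procedure correction. The classification mismatch between Section 12.8 and Section 10 is definite. The recall-time difference ranges from none to 48 hours, or is simply unstated, depending on the reading.

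A reader might go further in three ways that the documents do not support.

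- *That 24-hour return is confined to raised bilirubin.* The return sentence has no such condition, and the broad reading is tenable.
- *That patients with ALT/AST above 8 × ULN will be rechecked 48 hours late.* This needs the narrow and literal readings together, and 72 hours is an upper limit.
- *That patients stay on drug longer or that trial results are affected.* Section 10 governs withdrawal and leaves tapering to the investigator's judgment, so no exposure figure can be attributed to the wording. Efficacy analyses and the SAP liver tables do not use the 12.8 definition.

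The number of patients affected cannot be derived from the documents.

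**What to change.** Make three changes in Section 12.8.

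1. Replace "Abnormal values in AST and/or ALT concurrent with abnormal elevations in TBL that meet the criteria outlined above" with: *Results meeting any of the four criteria above*.
2. Limit the *alone*/72-hour sentence to elevations that meet none of the four criteria.
3. Add prothrombin time/INR to the repeat tests, at least when INR above 1.5 was the trigger.

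The cost is two reworded sentences, one added test and a note to sites. INR is derived from prothrombin time, which the laboratory panel already includes. The downside is some additional 24-hour recalls, important-medical-event reports and blood draws, for example in a child with ALT above 3 × ULN and fever, rash or vomiting. That deserves weight: enrollment starts at age two, and Section 9.1.9 cautions about further blood tests within a month of a study draw. The number of extra recalls cannot be derived from the documents. If the sponsor prefers a tiered recall with bilirubin as the faster tier, 12.8 should state a class and a return time for each of the four criteria.
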